1 BACKGROUND AND RATIONALE

Children with neurodevelopmental disorders such as cerebral palsy (CP) and autistic spectrum disorder (ASD) are found to have poor sleep.^{i,ii,iii,iv} Poor sleep in children with these long-term neurodevelopmental conditions may lead to worsening spasticity, increased caregiver burden and poorer quality of life.^{v,vi}

Use of Melatonin and other pharmacological sleep aids, treatment of obstructive sleep apnoea and application of sleep systems are some of the conventional ways to treat sleep problems in these children. In recent years, non-invasive brain stimulation such as transcranial electrical stimulation (TES) has emerged as a potential modality treatment to improve sleep in adult patients with major depressive disorders, bipolar disorders, migraine and Parkinson's disease.^{vii,viii,ix,x} TES involves the application of mild electrical current by placing electrodes on the scalp, resulting in the modulation of membrane potentials of the neurons in the underlying brain cortex.^{xi} TES of frontal brain regions where sleep slow oscillations originate, has been found to enhance spontaneous slow oscillatory EEG activity which induces sleepiness, ameliorating sleep quality and extending sleep duration.^{xii,xiii,xiv} TES may be delivered in the form of transcranial direct current stimulation (tDCS), transcranial alternating current stimulation (tACS) or transcranial pulsed current stimulation (tPCS). tPCS has increasingly gained attention as a novel safe and cost-effective treatment modality for spasticity in children with CP and for improvement of gait in adults with Parkinson's Disease.^{xv,xvi} This mode of therapy could serve as a potential alternative for pharmacotherapy in treatment of insomnia in children with neurodevelopmental disorders.^{xvii,xviii} However, most studies on sleep intervention used subjective sleep questionnaires and the use of any form of TES to improve sleep has not been studied in children. Thus, we aim to objectively evaluate whether tPCS can improve sleep in children with neurodevelopmental disorders, as compared to Melatonin.

1.1 General Introduction

tPCS is a form of TES that delivers unidirectional pulsed currents at a predetermined frequency to the brain cortex, as opposed to the direct current provided by tDCS. (refer Figure A device) It has been demonstrated that tPCS increases endogenously generated brain oscillations in a frequency-specific manner and facilitates interhemispheric connectivity.^{xix,xx,xxi,xxii} In recent studies, tPCS has shown to improve spasticity in children with CP and improve gait and balance in adults with Parkinson's Disease.^{xv,xvi} It has been postulated that tPCS may also be used to treat sleep difficulties by modulating dysfunctional inter-hemispheric coordination within the brain's default mode network and visual pathway, thought to be the core predisposing factors in the aetiology of primary insomnia.^{xxiii}

1.2 Rationale and Justification for the Study

Sleep disturbance is a common problem in children with neurodevelopmental disorder. Poor sleep leads to worsening spasticity and behaviour and can also affect learning and daytime engagement in school and with family members. Many families seek effective and safe interventions to improve sleep of their children with neurodevelopmental disorder. Use of Melatonin is a safe treatment option but some children may require more sedating pharmacological options to sleep and these medications are not without side effects if on long-term use. A safe and non-invasive intervention that can improve sleep in children with neurodevelopmental disorder is needed.

1.2.1 Rationale for the Study Purpose

Considering the clinical need to improve sleep in children with neurodevelopmental disorder and the high safety profile of non-invasive TES in children^{xxiv,xxv,xxvi} and the potential benefit of high frequency transcranial pulsed current stimulation applied at the cerebellum to modulate sleep-cycles, we aim to study the effectiveness in improving sleep in children with neurodevelopmental disorder.

1.2.2 Rationale for Doses Selected

tPCS has been shown to reach subcortical brain targets like the hippocampus from surface application on the cortex, to the extent that the hippocampus is associated with deep sleep and is sensitive to **400Hz** current stimulation in the induction of LTP, there is a possibility that **400Hz** tPCS may modulate sleep stages via influencing plasticity of the hippocampal formation.^{xxvii,xxviii}

The **cerebellum** displays various sorts of rhythmic activities that covers high-frequency oscillations, thus artificial resonance similar to intrinsic rhythms (400hz is within the high frequency category) may entrain intrinsic oscillations of the cerebellum based on resonance theory.^{xxix,xxx,xxxii,xxxii} Preliminary studies have shown that the tDCS in the **prefronto-cerebellar area** improves sleep quality in euthymic bipolar patients.^x The human **cerebellum** is easily accessible to non-invasive stimulation such as TES due to its anatomical location, and less painful compared to stimulating the prefrontal brain regions, making it more tolerable in children.^{xxxiii}

The low intensity current delivered by tPCS is between **1mA** to 2mA, about 800-1000 times weaker than conventional electroconvulsive therapy used in treating neuropsychiatry diseases. The working mechanism of tPCS has been suggested to involve the induction of static and dynamic current components to modulate transmembrane neuronal potentials, which can influence the “excitability-inhibitory balance” of cortical brain areas and regulate homeostasis in complex internal systems.^{xxix}

Based on safety recommendations of TES in children, current intensities of **~1mA** are often used, but trials up to 2 mA without serious adverse effects have been reported.^{xxxiv}

High frequency **400Hz, cerebello-cerebral** tPCS at **1mA, 30mins per day over 12 weeks**, has been tested in a study on 63 children with Cerebral Palsy, age 2 to 12 years old, to improve gross motor functions and spasticity, with no adverse event reported.^{xxv}

1.2.3 Rationale for Study Population

Preliminary studies have shown that tPCS was effective in improving spasticity in children with cerebral palsy while tDCS was effective in improving behaviour in children with ASD.^{xxv,xxxv,xxxvi} This study will focus on effectiveness in sleep in this group of population.

1.2.4 Rationale for Study Design

The unique Two-Period, Four-Sequence (Balaam's) design is used in this crossover trial in which each subject serves as his or her own control. Therefore the estimated treatment differences tend to have less variability than that observed in a parallel design. Smaller variability leads to a smaller sample size. Also, the repeated- measurements feature of a crossover design eliminates the need for a lengthy run-in or baseline period. Moreover, Balaam's design is a hybrid of a crossover design and a parallel design, whereby the estimated treatment difference is unbiased even in the presence of unequal carryover

effects.^{xxxvii}

HYPOTHESIS AND OBJECTIVES

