2 STUDY POPULATION

2.1 List Number and Nature of Subjects to be enrolled

[figure not shown]
Based on a two-sided paired t-test at 80% power and 5% one-sided alpha with 20% drop-out rate, a sample size of 40 is required to detect 20% improvement in primary end-point (total sleep time), assuming 15% standard deviation.

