3 STUDY DESIGN

Figure C: Study Design

At baseline (week 0), all patients will do a one-week sleep actigraphy and complete SDSC questionnaire. At week 1, patients will be randomised to one of the 4 treatment regimen that is determined by the first period of the sequence they are assigned to. Re-evaluation with sleep actigraphy and SDSC questionnaire will be done at week 4, 6 and 10. At week 7, the patients will cross over to the treatment for the second period of the sequence they are assigned to. Over the 10-week period, sleep diary will also be completed daily.

10 patients will receive dose-appropriate Melatonin over 8 weeks (Group A), 10 patients will receive 40 sessions of home-based tPCS over 8 weeks (Group D), 10 patients will receive 4 weeks of Melatonin then cross over to receive 4 weeks of 20 sessions of home-based tPCS (Group B) and 10 patients will receive 4 weeks of 20 sessions of home-based tPCS then cross over to receive Melatonin over 4 weeks (Group C).

There will be a washout period of 2 weeks (week 5 and 6) between cross over. Those on a Melatonin group cross over will also go through the same washout period.

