8 SAMPLE SIZE AND STATISTICAL METHODS

8.1 Determination of Sample Size

In an inequality test on data from the Balaam's crossover design, a sample size of 32 achieves 83% power at a 5% significance level when the absolute difference between the two treatment means is 0.2 and the within-subject standard deviation is 0.15. To account for 20% drop-out rate, a sample size of 40 (10 in each arm) is required.

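### Section 1.2.4 credits every child with being their own control and promises precision and carry-over protection together; only half the children cross over, and the precision depends on an estimator the protocol does not state

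*Protocol*

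**What the plan says.** Section 1.2.4 argues in three steps. It says that "each subject serves as his or her own control". It infers lower variability than in a parallel design and concludes that "Smaller variability leads to a smaller sample size". It then adds that Balaam's design is a crossover-parallel hybrid whose treatment estimate is unbiased even when carry-over differs between treatments.

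Section 3 sets out four sequences of 10 children. Group A takes Melatonin in both periods, B takes Melatonin then tPCS, and C takes tPCS then Melatonin. For the remaining sequence the text reads "10 patients will receive 40 sessions of home-based tPCS over 8 weeks (Group D"). Every child has a week of actigraphy at week 0, before treatment, and again at weeks 4, 6 and 10.

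Section 8.1 sizes the trial for Balaam's design: "a sample size of 32 achieves 83% power at a 5% significance level". The inputs behind this are a tPCS-Melatonin difference of 0.2 and an SD within children of 0.15. Dropout of 20% then raises the 32 to 40, or 10 per sequence.

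For the comparison of treatments, Section 8.2 plans independent t-tests. It mentions no period effect, carry-over effect or baseline adjustment.

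**The concern.** Groups A and D never receive the other treatment, so they yield no within-child tPCS-Melatonin difference. Their role in Balaam's design is different: they allow period and carry-over effects to be subtracted from the differences seen in B and C. That subtraction gives the protection against carry-over, and it costs variance. An argument that presents lower variance and carry-over protection as joint consequences of the design is therefore incomplete until it says which estimator is meant.

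Two things are at stake. A reader may take the result as a within-child comparison in 40 children when 20 provide one. And the second period and the two-week washout are justified partly by a precision gain that may not be realised, because the analysis that would realise it is not the one Section 8.2 describes.

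**Working it through.** **Inputs.** From Section 8.1: 32 evaluable children (8 per sequence), difference 0.2, within-subject SD sw = 0.15, 5% level. From Section 3: the four sequences and the week-0 recording. The within-child correlation rho of total sleep time is not given. I assume it is equal across weeks 0, 4 and 10 and show 0.3 to 0.9.

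**1. Children who cross over.** B + C = 10 + 10 = 20 of 40.

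**2. The carry-over-free within-child contrast.** Let d be period 2 minus period 1, with period effect p, tPCS-Melatonin effect t, and carry-over cM (Melatonin) or cT (tPCS). The expected values of d are:
- A: p + cM
- B: p + t + cM
- C: p - t + cT
- D: p + cT

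So B - A = t and D - C = t, whatever cM and cT are. The contrast is ½[(B - A) + (D - C)]. Each sequence mean of d has variance 2·sw²/8, so the contrast has variance ¼ × 4 × 2·sw²/8 = 2 × 0.0225/8 = 0.005625, and SE 0.075. This does not depend on rho.

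**3. Reproducing the 83%.** 0.2/0.075 = 2.67. With a noncentral t on 4 × 8 - 3 = 29 degrees of freedom, power is 83.1% at one-sided 5% and 73.2% at two-sided 5%. The stated 83% therefore matches this contrast at one-sided 5%. Dropout: 32/0.8 = 40, as stated.

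**4. A parallel comparison of the same 32 children at week 4 (16 v 16).** The total variance is sw²/(1 - rho).
- Change from week 0: variance 2·sw² × 2/16 = 0.005625, SE 0.075.
- Adjusted for week 0 (ANCOVA): variance [sw²/(1 - rho)](1 - rho²)(2/16) = sw²(1 + rho)/8.
- Unadjusted: variance [sw²/(1 - rho)](2/16).

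**5. The four-sequence design with a fuller estimator.** Generalised least squares with treatment, period and carry-over terms, using between-child as well as within-child information from weeks 4 and 10, and week-0 total sleep time as baseline.

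| rho | Within-child, carry-over-free | Parallel, unadjusted | Parallel, week-0 adjusted | Model with carry-over, no week 0 | Model with carry-over and week 0 |
|---|---|---|---|---|---|
| 0.3 | 0.075 | 0.063 | 0.060 | 0.044 | 0.042 |
| 0.5 | 0.075 | 0.075 | 0.065 | 0.049 | 0.045 |
| 0.7 | 0.075 | 0.097 | 0.069 | 0.056 | 0.047 |
| 0.9 | 0.075 | 0.168 | 0.073 | 0.067 | 0.048 |

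The last column is 36% (1 - 0.0483/0.075) to 44% (1 - 0.0422/0.075) below the contrast that matches the sizing.

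**6. The price of carry-over protection within children.** If carry-over is assumed absent, the within-child estimate from the same four groups has SE 0.053. An ordinary two-sequence crossover of 32 children would have sqrt(2 × 0.0225/32) = 0.0375. The carry-over-free contrast has four times that last variance (0.075² / 0.0375² = 4).

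**The case against.** A reader might infer that the design lacks the properties claimed for it and that the smaller-sample claim should be struck out. The documents do not support that. Step 2 shows that unbiasedness under additive carry-over is real. Step 5 shows that the four-sequence design, well analysed, beats the week-0-adjusted parallel comparison at every rho examined, even with carry-over terms in the model. The variance ratio is about 2.1 at rho 0.3 (0.0605²/0.0422²) and 2.3 at rho 0.9 (0.0731²/0.0483²). Precision and robustness can hold together. This part of the objection stands, and the claim should be qualified rather than deleted.

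The choice of comparator also matters. Section 1.2.4 is hedged and mentions no baseline adjustment, and against an unadjusted parallel comparison even the 0.075 contrast wins once rho exceeds 0.5. That is correct, but every child has week-0 actigraphy, so the adjusted comparison is the fair one. Its advantage is modest at high rho and, with the finite-sample factor 1 + 1/(N - 4), ends near rho 0.93. It also needs the equal-correlation assumption: in general it requires corr(week 4, week 10) below (1 + corr(week 0, week 4)²)/2, for example below 0.625 when the latter correlation is 0.5.

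Section 8.1 names no contrast and no sidedness, so tying its 83% to this contrast is an inference from the arithmetic. It is the match found at one-sided 5%; Section 2.1 does not settle sidedness, since it refers to a "two-sided paired t-test at 80% power and 5% one-sided alpha".

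Finally, Section 3 lists Groups A and D openly, Section 1.2.4 calls the design a hybrid, and model detail may sit in an analysis plan not seen here. The first two limit how far a reader would be misled, but they do not make the own-control sentence true for half the children. On the third, the point is not that detail is absent: Section 8.2 does state the between-treatment test, and as described it is not an analysis that delivers what Section 1.2.4 promises.

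**Conclusion.** The point holds in a limited form. The own-control statement is untrue for 20 of 40 children under any model. The precision argument is true only for some estimators. For the within-child contrast that reproduces 83% at one-sided 5%, precision is equal to a parallel comparison of change from week 0 (0.075 each) and worse than one adjusted for week 0 (0.060 to 0.073), assuming rho of 0.3 to 0.9 and equal correlations across weeks. A carry-over-adjusted model that also uses between-child information and the week-0 recording reaches 0.042 to 0.048 under the same assumptions, but the protocol does not state it and the t-tests in Section 8.2 are not it. The defect is one of rationale and matching analysis. It is no argument against the design or for a different number of children.

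**What to change.** In Section 1.2.4, say that children in Groups B and C act as their own controls; that Groups A and D allow period and carry-over effects to be separated from the treatment effect; and that any precision or sample-size advantage over a parallel design depends on the estimator and on what is assumed about carry-over. Keep the claim in that conditional form.

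In Section 8.2, name the primary tPCS-Melatonin estimate for total sleep time: a mixed model with treatment, period and carry-over terms, using between-child and within-child information and adjusting for week-0 total sleep time. State the assumed covariance structure.

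The cost is protocol wording and slightly more analysis work, with no change to allocation, visits or sample size and no new data, since the week-0 recording is already planned for every child. The price is reliance on the model's covariance assumption, which the simple within-child contrast largely avoids; that contrast can be reported alongside as a sensitivity analysis.

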1.3 Hypothesis

tPCS is effective in improving total sleep time in children with neurodevelopmental disorder.

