1.4 Primary Objectives

The primary objective is to assess the effectiveness of tPCS in improving total sleep time by 20% in children with neurodevelopmental disorder, compared with using Melatonin.

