2.3 Inclusion Criteria

- Aged 4-16
- Neurodevelopmental disorder including cerebral palsy, autistic spectrum disorder, neurogenetic syndrome.
- Patients whose pre-intervention sleep questionnaire total score more than 46 and/or pre-intervention sleep questionnaire T-score more than 70 in any sleep domain
- Children agree to tPCS as per procedure and consent to the study, including need to shave hair at the site of stimulation at the occiput (refer Figure B)
- Parents/carers agree to bring children to KKH for tPCS as per visit schedule and procedure
- Medical practitioner's approval

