8.2 Statistical and Analytical Plans

The SPSS® 25.0 software (IBM, Armonk, New York, United States) will be used, with statistical significance defined as a p-value of <0.05 . Independent t-tests will be conducted to compare differences in outcomes between the two treatment groups; Wilcoxon signed-rank test will be used to compare continuous variables at start and end of treatment. Average of actigraphic measurements were used to compare effects of treatment on sleep parameters. One-way Repeated Measure ANOVA will be conducted to assess changes in outcomes and patient scores within the group across the timepoints. Non-parametric testing will also be conducted to observe for significant differences in patient outcomes within the groups at each timepoint.

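### The hypothesis in 1.3 claims an absolute tPCS effect, which the Melatonin-controlled design can show only by superiority over Melatonin, yet 8.2 ranks uncontrolled within-group tests beside the randomised contrast

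*Protocol*

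**What the plan says.** - **Hypothesis (1.3):** "tPCS is effective in improving total sleep time in children with neurodevelopmental disorder". No comparator is named.
- **Primary objective (1.4):** "improving total sleep time by 20% in children with neurodevelopmental disorder, compared with using Melatonin". The background (Section 1) gives the same aim: "whether tPCS can improve sleep in children with neurodevelopmental disorders, as compared to Melatonin".
- **Design (Section 3):** four sequences, each giving Melatonin or tPCS in each of two four-week periods, with a two-week washout between them. No sequence contains a sham or untreated treatment period.
- **Selection (2.3):** entry requires a "pre-intervention sleep questionnaire total score more than 46" and/or a T-score above 70 in any sleep domain.
- **Blinding (3.1, 5.5):** patients are not blinded; the actigraphy reader and the analyst are.
- **Sample size (8.1):** an inequality test of the difference between the two treatment means; 32 children, raised to 40 for drop-out.
- **Analysis (8.2):** "Independent t-tests will be conducted to compare differences in outcomes between the two treatment groups". Also: "Wilcoxon signed-rank test will be used to compare continuous variables at start and end of treatment". One-way repeated-measures ANOVA and further non-parametric tests within the groups follow. A single threshold, p<0.05, covers all of them, and the section does not say which result decides the hypothesis.

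**The concern.** Sections 1.3 and 1.4 make different claims. The first is that tPCS works; the second is that it does better than an active treatment. Superiority over Melatonin would support both, at least if Melatonin does not itself shorten sleep. If the two treatments come out alike, only the start-to-end changes are left to speak to 1.3, and these have no concurrent control.

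Start-to-end change mixes any treatment effect with regression to the mean, the passage of time and the expectations of families who know what they are receiving. Regression to the mean bears most directly on the SDSC: it is the sleep questionnaire measured at baseline and again at weeks 4, 6 and 10, and it appears to be the one used for selection. At stake is what the trial may conclude. As 1.3 and 8.2 stand, a significant within-group change could be reported as confirming the hypothesis although neither treatment had worked.

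**Working it through.** **1. What the plan's own power figure refers to.** Inputs from 8.1: difference 0.2, within-subject SD 0.15, 32 children, so n = 8 per sequence. For Balaam's design:

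- SE = 0.15 × √(2/8) = 0.075
- noncentrality = 0.2 / 0.075 = 2.667
- df = 4 × 8 − 3 = 29

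Power from the noncentral t is 83.1% at one-sided 5%, which reproduces the stated 83%. (At two-sided 5% it is 73.2%; that is a separate matter.) Drop-out: 32 / 0.8 = 40. The trial is thus sized for tPCS versus Melatonin, and naming Melatonin in 1.3 changes no sample-size figure.

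**2. SDSC: size of a spurious fall.** The protocol gives no mean, SD or test-retest correlation for the SDSC total, so these are assumptions: SD 10, population mean μ of 40, 46 or 52, correlation r of 0.6 or 0.8, entry only by total above 46, the qualifying score used as the starting value, no treatment effect, and 20 children per treatment in period 1 (two sequences of 10).

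With a = (46 − μ)/10 and λ = φ(a)/[1 − Φ(a)], the expected fall on re-measurement is (1 − r) × 10 × λ. For example, μ = 40 gives a = 0.6 and λ = 1.215, so r = 0.6 gives 0.4 × 10 × 1.215 = 4.9 points.

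Simulation gives the share of trials with a significant result at 5%. For the start-to-end tests only results in the improving direction are counted (nominal 2.5%); for the between-group t-test on changes, both directions (nominal 5%).

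| μ | r | Expected fall | Paired t | Wilcoxon | Between-group t |
|---|---|---|---|---|---|
| 40 | 0.6 | 4.9 | 70% | 67% | 5% |
| 40 | 0.8 | 2.4 | 40% | 38% | 5% |
| 46 | 0.6 | 3.2 | 37% | 35% | 5% |
| 46 | 0.8 | 1.6 | 20% | 19% | 5% |
| 52 | 0.6 | 1.8 | 14% | 14% | 5% |
| 52 | 0.8 | 0.9 | 10% | 9% | 5% |

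The fall is shared by the randomised groups, so the between-group test keeps its level.

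**3. Total sleep time: mechanism only.** Children are not selected on total sleep time. Its regression depends on its correlation with the questionnaire, which the protocol does not give. To show the mechanism, take the SD of change as 0.15 × √2 = 0.212, 20 children per treatment, no difference between treatments, and a shared improvement of assumed size:

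| Shared shift (fraction of baseline) | Start-to-end Wilcoxon significant | Between-group t significant |
|---|---|---|
| 0 | 4% | 4% |
| 0.05 | 16% | 6% |
| 0.10 | 51% | 5% |
| 0.15 | 84% | 6% |

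Nothing in the protocol says which row applies.

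**The case against.** The strongest reply is that the trial does have a controlled test of tPCS. A reader might infer from 1.3 that only the within-group tests address the hypothesis. The document does not support that: the background, 1.4, the randomisation, the sample size and the first test named in 8.2 all concern tPCS against Melatonin, and superiority there would bear on 1.3. This stands, and it limits the point to the mismatch in wording and the equal footing of the tests.

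The figures are also open to challenge, and fairly so:

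- The SDSC is a secondary outcome. The primary endpoint is actigraphic and is read blind.
- The T-score route lets in children with totals of 46 or less, so truncation at 46 is not the exact entry rule.
- The protocol does not say that one SDSC administration serves for both screening and baseline.
- Period 2 starts from a new week-6 measurement that was not used for selection.
- With a population mean of 52, the false-improvement rate falls to about 9% to 14%.

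A reader might further infer that a null difference is to be reported as tPCS working as well as Melatonin, since the background says tPCS "could serve as a potential alternative for pharmacotherapy". That sentence is motivation. The protocol plans no equivalence or non-inferiority claim, so the absence of a margin is not an error.

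Finally, marking analyses as confirmatory or descriptive is often left to a statistical analysis plan. That alone would not be a finding. Here, however, the protocol itself fixes a hypothesis that its randomised comparison does not match, together with uncontrolled tests that could be used to claim it.

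**Conclusion.** The point holds in this form. Sections 1.3 and 1.4 do not agree, and the design cannot establish an absolute tPCS effect except through superiority over Melatonin. The within-group tests in 8.2, given the same standing as the between-treatment test, can be significant without any treatment effect.

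The exposure is chiefly on the SDSC: roughly 9% to 70% false improvement in the illustration, against about 5% for the between-group test. That range rests on an assumed SD, mean and correlation, on entry by total score alone, and on period 1 only. For total sleep time the risk is smaller and cannot be quantified from the protocol.

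The randomised contrast removes shared regression to the mean and time effects. It does not remove differential expectation, because families know which treatment the child is having; this matters most for parent-rated outcomes. The point should be addressed, since it alters what the trial may conclude, but it does not invalidate the comparison with Melatonin.

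**What to change.** 1. Restate 1.3 as tPCS compared with Melatonin on total sleep time, consistent with 1.4, including how the 20% is meant.
2. In 8.2, make the randomised tPCS–Melatonin contrast, reported with its 95% confidence interval, the sole basis for effectiveness conclusions on total sleep time and SDSC.
3. In 8.2, label the start-to-end tests and the within-group ANOVA descriptive.
4. Acknowledge as a limitation that the contrast is open-label, so differential expectation may remain in parent-rated outcomes.

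The cost is wording only: no extra data or visits, and the sample size stays at 32, raised to 40. The downside is a narrower claim. If tPCS does not prove superior to Melatonin, the trial cannot conclude from the within-group changes that tPCS is effective.
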